11.4.2.3 Persistent Arrhythmias at 30 Days and 3 Months

12-lead ECGs will be used to confirm any persistent arrhythmias at 30 days and 3 months post-study drug.

Assessments of persistent arrhythmias will be listed and the number of subjects with persistent arrhythmias will be tabulated by treatment group at 30 days and 3 months. Odds ratio will be calculated for each FDY-5301 treatment group against the placebo group, along with its 95% confidence interval.

The same summarization method and statistical analyses will be repeated by baseline TIMI flow (grade 1 and lower, or, grade 2 and 3) and infarct type (anterior or other).

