7 STUDY DESIGN

This is a Phase 2A, randomized, double-blind, placebo-controlled, multi-center study that will evaluate the safety, efficacy, and PK of FDY-5301 in patients with acute STEMI undergoing PCI.

Patients will receive either FDY-5301 or volume matched placebo after informed consent is obtained and a STEMI diagnosis has been made based on clinical and electrocardiogram (ECG) findings, within an hour prior to myocardial reperfusion.

A minimum of 80 evaluable patients will be enrolled and randomized in a 1:1:1:1 ratio to receive a single dose of 0.5, 1.0, or 2.0 mg/kg FDY-5301 or placebo.

All patients will have an early and late (3 month) cardiac magnetic resonance (CMR) and 14 days of arrhythmia monitoring and will be followed up for safety and efficacy for up to 6 months. Patients will be monitored in hospital, and return for clinic visits 14 days, 30 days, and 3 months post PCI (Figure 1).

Figure 1: Study Diagram

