9 SAMPLE SIZE JUSTIFICATION

As this is the first clinical study of FDY-5301 in patients, safety is the primary focus. For this reason, the goal is to expose a limited number of patients to FDY-5301 while still powering the study to detect significant differences in efficacy measures across groups. A total sample size of 80 patients will provide 80% power to detect a 37% reduction in infarct size (INF) / ventricular volume (VV) assuming a standard deviation (SD) of 10%, a 24% increase in MSI assuming a SD of 20% and a 39% reduction in Troponin area under the curve (AUC) with an SD of 60%. Equal variance was assumed among groups with an unbalanced allocation of patients to placebo (n = 20) and overall FDY-5301 treatment groups (n = 60).

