11 STATISTICAL METHODOLOGY

11.1 General

Data listings will be provided for the ITT Population. Summary statistics and statistical analyses will be performed for patients included in the relevant analysis populations.

For continuous data, summary statistics will include the arithmetic mean, arithmetic standard deviation, median, minimum, maximum, and number. For log-normal data (eg, the PK parameters: AUCs and maximum observed concentration [C_{max}]), the geometric mean and geometric coefficient of variation (CV%) will also be presented. For categorical data (i.e. ST-segment resolution and persistent arrhythmias), frequency counts, percentages and odds ratios will be presented, where applicable. Data listings will be provided for all patients up to the point of withdrawal, with any patients excluded from the relevant population highlighted. For the calculation of summary statistics and statistical analysis, unrounded data will be used.

Missing values will not be imputed.

Data analysis will be performed using SAS® Version 9.4 or higher.

Analysis Data Model (ADaM) datasets will be prepared using Clinical Data Interchange Standards Consortium (CDISC) ADaM Version 2.1, and CDISC ADaM Implementation Guide Version 1.1. Pinnacle 21 Community Validator Version 2.1.2 will be utilized to ensure compliance with CDISC standards.

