11.4.2.2 Proportion of Patients with ST-segment Resolution at 4 hours Post-study Drug

12-lead ECGs will be used to obtain baseline ST-segment elevation prior to treatment in order to evaluate ST-segment resolution 4 hours post-study drug.

ST-segment resolution will be defined as a reduction of the ST-segment elevation by 50% when compared to the baseline. Evaluation of the percentage of ST-segment resolution will be undertaken on the single worst ECG lead (defined as the lead with the maximal ST-segment elevation). Baseline is defined as the maximal ST-segment elevation obtained at Day 1 screening. Results will be categorized as either resolved or non-resolved.

The number of patients with ST-segment resolution will be tabulated by treatment group. Odds ratios will be calculated for each FDY-5301 treatment group (and overall) against the placebo group, along with its 95% confidence interval.

The same summarization method and statistical analyses will be repeated by baseline TIMI flow (grade 1 and lower, or, grade 2 and 3) and infarct type (anterior or other).

Clinician's ECG interpretation collected from the eCRFs will be listed.

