14 DATA PRESENTATION

14.1 Insufficient Data for Presentation

Some of the TFLs may not have sufficient numbers of patients or data for presentation. If this occurs, the blank TFL shell will be presented with a message printed in the center of the table, such as, “No serious adverse events occurred for this study.”

[figure not shown]

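### SAP 11.4.2.3 gives persistent arrhythmias no overall FDY-5301 versus placebo comparison, and its dose-level odds ratios may not be estimable if events are uncommon

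*SAP*

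**What the plan says.** SAP 6.2.1 names the proportion of patients with persistent arrhythmias at 30 days and 3 months as a secondary efficacy outcome. SAP 11.4.2.3 plans a listing and a table ("the number of subjects with persistent arrhythmias will be tabulated by treatment group at 30 days and 3 months"). The only between-group comparison follows: "Odds ratio will be calculated for each FDY-5301 treatment group against the placebo group, along with its 95% confidence interval". The same analysis is repeated by baseline TIMI flow and by infarct type, and SAP 11.4 runs it in both the ITT and the per-protocol population.

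The section just before it, on ST-segment resolution, is the other binary efficacy outcome. It is worded differently: "Odds ratios will be calculated for each FDY-5301 treatment group (and overall) against the placebo group, along with its 95% confidence interval".

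For categorical data in general, SAP 11.1 says that "frequency counts, percentages and odds ratios will be presented, where applicable". SAP 11.4.2.3 names no interval method, and neither document says how a zero cell is handled or provides a risk difference. On size, SAP 7 says: "A minimum of 80 evaluable patients will be enrolled and randomized in a 1:1:1:1 ratio".

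**The concern.** Two things stand out.

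First, the contrast on which the trial is sized is missing for this outcome. SAP 9 bases the sample size on 20 placebo patients against 60 on FDY-5301 combined. An overall comparison with placebo is planned for the primary arrhythmia rates (SAP 11.4.1), infarct size (11.4.2.1), ST-segment resolution (11.4.2.2), cardiac function (11.4.2.4), troponin (11.4.2.5) and biomarker concentrations (11.4.2.6). Among the secondary efficacy outcomes, only persistent arrhythmias lack it. SAP 13, on changes from the protocol, gives no reason.

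Second, an odds ratio from a small arm with few events can have a zero cell. The estimate is then 0, infinite or undefined, and the usual Wald interval does not exist. If persistent arrhythmias are uncommon, the planned comparison could be missing for some or all doses, although the data could still bound the difference in risk.

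**Working it through.** **Inputs from the documents.** Allocation is 1:1:1:1 with at least 80 evaluable patients (SAP 7), so 80/4 = 20 per arm, and the three doses together have 3 × 20 = 60, as in SAP 9. The protocol (14.1.4) allows up to 160 enrolled with about 50% drop-out: 160 × (1 − 0.5) = 80, which reproduces. If all 160 contributed, an arm would have 160/4 = 40. Missing values are not imputed (SAP 11.1), so the number analysed per arm should lie between about 20 and 40.

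**Input not in the documents.** Neither document states a rate of persistent arrhythmia. I assume a true rate p of 2%, 5%, 10% or 15%, equal in all arms. There is no planned figure for this outcome to reproduce; the 80% power in SAP 9 is for INF/VV, MSI and troponin AUC only.

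**Formulas.** Let q = (1 − p)^n be the chance that an arm of n patients has no event. The chance that every patient in an arm has one is negligible at these rates.

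- One dose-level odds ratio fails: 1 − (1 − q)².
- All three fail: q + (1 − q)q³, that is, no placebo event, or placebo events but none in any dose arm.

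Example, p = 5%, n = 20: q = 0.95^20 = 0.358. One fails: 1 − 0.642² = 0.59. All three fail: 0.358 + 0.642 × 0.358³ = 0.39.

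| Assumed rate | One fails, n = 20 | One fails, n = 40 | All three fail, n = 20 | All three fail, n = 40 |
|---|---|---|---|---|
| 2% | 89% | 69% | 77% | 49% |
| 5% | 59% | 24% | 39% | 13% |
| 10% | 23% | 3% | 12% | 1.5% |
| 15% | 8% | 0.3% | 4% | 0.2% |

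A given dose contrast fails more often than not only below a rate of about 6% at 20 per arm, or about 3% at 40 per arm. If the drug halves the rate, one dose-level odds ratio at 20 per arm fails in 75% of trials when the placebo rate is 5%, and in 44% when it is 10%.

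**Subgroups.** Stratum sizes are not stated. In an assumed stratum of 10 versus 10, one odds ratio fails with probability 84% at a 5% rate, 58% at 10% and 20% at 20%.

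**What pooling does.** The pooled odds ratio has a zero cell when placebo has no events, or when all three dose arms have none. These are the same events as all three dose-level odds ratios failing, so the last two columns also give its failure probability. Against a single dose contrast at 20 per arm, failure falls from 59% to 39% at a 5% rate. Pooling never rescues a trial in which all three dose contrasts fail.

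Pooling does improve precision. For a true odds ratio of 1 and a 10% rate, using expected counts, the SE of the log odds ratio is:

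- 20 versus 20: √(1/2 + 1/18 + 1/2 + 1/18) = 1.054, so the 95% interval is about exp(±1.96 × 1.054) = 0.13 to 7.9.
- 60 versus 20: √(1/6 + 1/54 + 1/2 + 1/18) = 0.861, so about 0.19 to 5.4.

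**What a risk difference does.** The Newcombe interval is finite with zero cells:

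- 3/60 versus 0/20: 5.0% (−11.4% to 13.7%)
- 2/40 versus 0/40: 5.0% (−4.5% to 16.5%)
- 6/120 versus 0/40: 5.0% (−4.2% to 10.5%)

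**The case against.** The strongest case for leaving the section alone has four parts.

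- *It follows the protocol.* Protocol 14.1.6 specifies dose-level odds ratios against placebo for categorical outcomes. This is true, and it is a reason to keep the odds ratio. It does not explain the gap, because the SAP went beyond that rule for ST-segment resolution and did not do so here.
- *The rate is unknown.* This stands. At 15% or more, a zero cell in the full set is unusual (8% or less), so non-estimability can only be stated conditionally.
- *Failure presumes a Wald interval.* This also stands in part. With one zero cell an exact method still gives a finite bound on one side; only 0 versus 0 is uninformative, which at a 5% rate has probability 0.358² = 13% at 20 per arm and 2% at 40. But the SAP does not name an exact method.
- *The outcome is exploratory and the counts are printed.* This is true: a reader could build the pooled contrast or a risk difference from them. It limits the importance of the point.

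A reader might also infer from SAP 14.1, under which "the blank TFL shell will be presented with a message printed in the center of the table", that a zero cell leads to a blank table. The documents do not support that. The rule is for outputs with too few patients or data to present, and here counts and percentages would still be shown beside an odds ratio that cannot be given.

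**Conclusion.** The omission of the overall comparison is a plain inconsistency within the SAP and needs no assumption. The risk of a missing estimate depends on the event rate: considerable at 2% to 5%, modest at 10% with 20 per arm, and small at 15%. It is greater in the TIMI and infarct-type tables.

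A reader might go further and conclude that the outcome would often yield no comparison at all. That requires all three dose-level odds ratios to fail, with probability 77% or 39% at 20 per arm, and 49% or 13% at 40 per arm, for rates of 2% or 5%. The chance that at least one of the three fails, q + (1 − q)(1 − (1 − q)³), is larger (99% or 83%, and 91% or 42%), but it does not measure that loss. Without a rate in the documents, an unqualified *often* is not supported.

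The figures assume equal true rates across arms, 20 to 40 analysed per arm and a Wald odds ratio. I rate this as a cheap improvement, not a flaw that threatens the trial's conclusions.

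**What to change.** In SAP 11.4.2.3:

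1. Add the overall FDY-5301 group to the odds ratio sentence, matching 11.4.2.2. The reason is precision and consistency; it is not a remedy for zero cells.
2. Keep the odds ratio that the protocol specifies. Add one sentence giving the risk difference with a Newcombe or Miettinen-Nurminen 95% interval, naming which of the two, for each dose and overall.
3. Apply the same method in the TIMI flow and infarct-type tables, and state that an odds ratio with a zero cell will be shown as not estimable beside the risk difference.

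The cost is a sentence or two in the SAP and one more estimate per table, with no new data. The intervals will be wide at these sizes and should be presented as bounds, not as evidence of no difference.

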11.4.2.4 Measures of Cardiac Function by CMR

The EDV, ESV, FS and EF will be assessed at 72 ± 24 hours post-study drug and 3 months post-study drug.

Summary statistics will be produced for the observed values along with changes from baseline by each treatment group and the overall FDY-5301 group for each parameter. The baseline is defined as the measurement taken at the 72 hour timepoint.

For the changes from baseline for each of these parameters, a single pairwise comparison will be performed to analyze the results between all three FDY-5301 groups (overall) and placebo. An unpaired Student's T-test will be used for the pairwise comparison if the data are normally

distributed and a Mann-Whitney rank test will be used for nonparametric data. Normality will be assessed based on the Shapiro-Wilk test at the 5% level. If the unpaired Student's T-test was selected, the difference in means and its 95% confidence interval will be produced.

The parameters from each group will then be tested using a one-way ANOVA to obtain a common variance followed by a Dunnett's post-test to separately compare each FDY-5301 dose group to placebo.

The same summarization method and statistical analyses will be repeated by baseline TIMI flow (grade 1 and lower, or, grade 2 and 3) and infarct type (anterior or other).

11.4.2.5 Serum Levels of Troponin

The troponin AUC₀₋₄₈ will be derived from the serum levels of troponin collected at the following timepoints: Predose, 4, 12, 24 and 48 hours post-study drug. AUC₀₋₄₈ will be calculated using the linear trapezoidal method. Where possible, the derivation will be carried out using actual post-dose times recorded. If actual times are missing, nominal times may be used with sponsor approval.

Summary statistics (also including geometric means and geometric coefficient of variation [CV] %) for the serum levels will be produced by each treatment group and the combined FDY-5301 group for the derived AUC₀₋₄₈. The summary statistics for troponin AUC₀₋₄₈ will be presented in a similar way.

The derived AUC₀₋₄₈ will be logarithmically transformed, and an unpaired Student's T-test will be used analyze its differences between all three FDY-5301 groups (overall) and placebo.

The logarithmically transformed AUC₀₋₄₈ from each group will then be tested using a one-way ANOVA to obtain a common variance followed by a Dunnett's post-test to separately compare each FDY-5301 dose group to placebo.

The arithmetic least squares means of the treatment differences will be back-transformed to provide the geometric means and its 95% confidence interval.

The same summarization and statistical analyses will be repeated by baseline TIMI flow (grade 1 and lower, or, grade 2 and 3) and infarct type (anterior or other).

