12.2.4 Troponin Levels

In order to calculate AUC 0-48 hours, serum troponin T levels will be measured at the following time points:

- Pre-study-drug
- 12, 24, 48 hours post-study drug

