14.1.4 Sample Size Estimation

Little data exists on the incidence of arrhythmias that occur over an extended period of time following AMI and monitoring strategies for this type of assessment have not been optimized in a clinical trial setting. The primary goal of our study is to characterize the occurrence of arrhythmias in this patient population for 14 days post-AMI and to determine the feasibility of using ambulatory patch ECG monitors to capture this data. These data should be regarded as exploratory with the objective of identifying a meaningful clinical end point that can be easily measured in future, pivotal studies that are adequately powered to detect differences across treatment groups.

Estimating a drop-out rate of approximately 50%, we will need to enroll up to 160 patients in order to obtain a final total sample size of 80 patients. A final sample size of 80 patients will provide 80% power to detect a 37% reduction in INF/VV assuming an SD of 10%, a 24% increase in MSI assuming an SD of 20% and a 39% reduction in Troponin AUC with an SD of 60%. Equal variance was assumed among groups with an unbalanced allocation of patients to placebo (n=20) and combined FDY-5301 treatment groups (n=60).

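### The troponin AUC0-48 comparisons are valid but leave the scheduled predose troponin unused, giving up precision that a prespecified covariate could recover at almost no cost

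*SAP*

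**What the plan says.** Protocol 12.2.4 states that "serum troponin T levels will be measured at the following time points": before study drug, then "12, 24, 48 hours post-study drug". SAP 11.4.2.5 builds the AUC by the linear trapezoidal rule from a different list, "Predose, 4, 12, 24 and 48 hours post-study drug". The predose value is a term of the AUC on either list.

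The AUC is log-transformed. For pooled FDY-5301 against placebo, "an unpaired Student's T-test will be used analyze its differences between all three FDY-5301 groups (overall) and placebo". The four groups are then "tested using a one-way ANOVA to obtain a common variance followed by a Dunnett's post-test", each dose against placebo. No covariate enters either step, and no baseline-corrected AUC is planned. Protocol 14.1.6 also names only unadjusted tests for continuous outcomes. Repeating the analysis by TIMI flow and infarct type is a subgroup display, not adjustment for predose troponin.

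Troponin AUC is one of three outcomes behind the sample size. SAP 9 states "A total sample size of 80 patients will provide 80% power" for, among others, "a 39% reduction in Troponin area under the curve (AUC) with an SD of 60" per cent, with 20 placebo and 60 pooled active patients; Protocol 14.1.4 gives the same figures.

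**The concern.** Inclusion allows entry up to 12 hours after symptom onset (Protocol 6.1). Predose troponin is therefore likely to vary widely between patients, for reasons the bolus cannot affect, and it plausibly predicts later troponin. An unadjusted test leaves that predictable part in the error term.

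At stake is the width of the interval for the pooled contrast and, more so, for the dose-level contrasts, where the arms are smallest. With 20 versus 60 patients, the chance difference in mean predose value has a standard deviation of sqrt(1/20 + 1/60) = 0.258 predose SDs. At an assumed rho of 0.5, a one-SD imbalance of that kind moves the log AUC contrast by 0.5 × 0.258 = 0.129 SD, against a planned effect of 0.65 SD. The unadjusted interval allows for this by being wider; adjustment would largely remove it.

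**Working it through.** **Inputs.** Effect 39%, SD 60%, 20 versus 60 (SAP 9, Protocol 14.1.4). Up to 160 randomised (Protocol 5.1), 1:1:1:1 (SAP 7). Alpha and sidedness are not stated for the sample size; two-sided 5% is taken here because SAP 11.4.2.5 reports 95% intervals. The correlation rho between log predose troponin and log AUC0-48 is not in the documents and is shown as a range.

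**Formula.** Noncentral-t power with noncentrality d / sqrt(1/n1 + 1/n2). Adjustment replaces d by d / sqrt(1 − rho²) and removes one degree of freedom.

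**The plan's figure first.** d = 39/60 = 0.65 and noncentrality = 0.65/0.2582 = 2.52. One-sided 5% gives 80.2%, which reproduces the stated 80%. Two-sided 5% gives 70.1%.

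**Variance.** Residual variance falls by rho²: 9%, 25% and 49% at rho 0.3, 0.5 and 0.7. Log-scale intervals narrow by 1 − sqrt(1 − rho²): 5%, 13% and 29%. Eighty adjusted patients are worth 80/(1 − rho²) unadjusted ones: 88, 107 and 157.

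**Power, two-sided 5%, 80 patients.** The log-scale rows read the 60% as a log SD of 0.6 (an assumption), so d = |ln 0.61|/0.6 = 0.824. The Dunnett row uses a simulated critical value of 2.40.

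| Comparison | Unadjusted | rho 0.3 | rho 0.5 | rho 0.7 |
|---|---|---|---|---|
| Pooled, 20 vs 60, d = 0.65 | 70% | 74% | 82% | 94% |
| Pooled, 20 vs 60, log SD 0.6 | 88% | 91% | 95% | 99% |
| Each dose, 20 vs 20, Dunnett, log SD 0.6 | 58% | 63% | 73% | 89% |

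Simulating the first row (20,000 trials per rho, t-test against ANCOVA) gave 70.1% against 73.3%, 70.2% against 81.8%, and 70.1% against 93.3%. At rho 0 it gave 70.3% against 69.7%, so a useless covariate costs about half a point.

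**Upper bound on numbers.** SAP 11.4 runs these analyses on ITT and repeats them on the per-protocol set. If all 160 randomised patients supply troponin samples, the split is 40 versus 120. At d = 0.65 the pooled test has 94% unadjusted, 96% at rho 0.3 and 98% at rho 0.5. Dunnett with 40 per arm and log SD 0.6 has 90% unadjusted and 97% at rho 0.5.

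**Direct weight of the predose value.** Under the trapezoid rule its weight is half the first interval. On the SAP times this is 2 of 48 hours (4.2%); on the protocol times, 6 of 48 hours (12.5%). Most of any gain therefore comes from correlation with later values, not from this term.

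**The case against.** The strongest reply is that nothing here is an error. Allocation is randomised, so the t-test is unbiased, holds its type I error, and has an interval that already reflects chance imbalance. The protocol calls these outcomes exploratory and prespecifies unadjusted tests, and the primary outcome is descriptive. The correlation is unknown; at rho 0.3 the pooled gain is about 4 points even with 80 patients. Some predose values may be unquantifiable, which would weaken a log-linear covariate. All of this stands, and it limits the point to efficiency.

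Several stronger readings are tempting, but the documents do not support them:

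- A reader might infer that the troponin result will be biased. Randomisation rules that out.
- A reader might start from 80% power at two-sided 5% and credit adjustment with a rise to 90%. The plan's inputs give about 70% two-sided and reach 80% only one-sided.
- A reader might treat 20 placebo patients as the fixed analysis size. The 80 are patients with complete arrhythmia and infarct-size data (Protocol synopsis), while troponin needs samples only to 48 hours and ITT could reach 40 placebo patients.
- A reader might say that troponin is singled out, because SAP 11.4.2.6 compares change from baseline for other biomarkers. That applies to concentrations by timepoint; the biomarker AUC0-48 gets the same covariate-free ANOVA.
- A reader might infer that the troponin Dunnett contrasts will decide the dose. Neither document says so.

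**Conclusion.** The point holds as a loss of precision on a secondary, exploratory outcome. A covariate that is already scheduled and cannot be affected by the drug is left out of every planned troponin test. The size depends on an assumed rho: small at 0.3, material at 0.5 or above. It is greatest for the dose-level contrasts with 20 per arm (58% to 73% at rho 0.5) and least for the pooled contrast if ITT approaches 160 patients (94% to 98% at rho 0.5). The conclusion assumes two-sided 5%, a roughly linear relation on the log scale, and predose values that are mostly quantifiable.

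Separately, the SAP's 4-hour troponin sample is not in the protocol's troponin schedule, and the two must be reconciled because the AUC depends on the times used.

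**What to change.** Before database lock and unblinding, amend SAP 11.4.2.5 so that the main analysis is one ANCOVA of log AUC0-48 on treatment group (four levels) with log predose troponin as covariate. Take the pooled FDY-5301 versus placebo contrast and the three Dunnett-adjusted dose contrasts from that model, as geometric mean ratios with 95% confidence intervals. State in advance the constant used for unquantifiable predose values (half the lower limit of quantification, for example) and how a missing predose value is handled. Keep the unadjusted t-test and ANOVA as a supporting table, and record the change in SAP 13. Reconcile the SAP and protocol troponin sampling times in the same revision.

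The cost is SAP wording, one model term and one residual degree of freedom, or about half a point of power if rho is 0. Patients without a predose sample may drop out of the adjusted model. They also lack the first term of the AUC, for which the section gives no rule, so a missing-predose rule is needed in any case. No new data, visits or patients are required.
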